9.2.4 Determination of Adverse Events (Clinical Events Committee, CEC)

In order to ensure that events reported as AEs meet clinically recognized and accepted standards and are reported in a uniform manner across sites, AEs that have been assessed by the site Principal Investigator to be device related, severe in nature, and/or meets the definition of one the primary safety endpoint events, will be reviewed and adjudicated by a CEC. Adjudication of reported adverse events will be performed by a multi-physician panel. Adjudication will be done against the standard of whether a reasonable attending nephrologist would attribute the AE to one of the causes listed as part of the Primary Safety Endpoint above. In the case of disagreement by the adjudication panel, determination will be made by majority vote. The CEC also will confirm those reported events indicated as such, do indeed meet the Safety Endpoint criteria. In addition, the CEC will periodically review all AEs, including those that are not included as a primary endpoint, to assess overall study safety.

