9 ADVERSE EVENT REPORTING

9.1 Adverse Event Definitions

9.1.1 Adverse Event (AE):

An adverse event (AE) is any undesirable medical occurrence in a clinical study Subject, whether it is considered to be related to the device or not, that includes a clinical sign, symptom or condition.

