9.1.5 Primary Safety Endpoint

This category includes the 8 pre-specified adverse events that will be analyzed as the Primary Safety Endpoint for the study:

- 1. Serious Adverse Event: any serious adverse event that:
 - Results in death,
 - Is life-threatening,
 - Requires hospitalization or prolongs existing hospitalization,
 - o Requires intervention to prevent permanent impairment or damage, or
 - \circ $\;$ Results in persistent or significant disability/incapacity.
- 2. Allergic Reaction: Type A, anaphylactoid or Type B dialyzer reactions to dialyzer, blood tubing or chemical disinfectant.
- 3. **Blood Loss**: blood loss resulting in hemodynamic compromise that leads to death, transfusion or fluid resuscitation with greater than 1 liter of crystalloid IV fluids.
- 4. **Hemolytic Reaction**: hemolytic reactions due to disinfectant exposure, dialysate temperature, mechanical failure or other device related causes.
- 5. Infection: any infection related to catheter, its tunnel or exit site, AV fistula, or AV graft.
- 6. Intra-Dialysis Event: a significant clinical event such as loss of consciousness, cardiac arrest, or seizure caused by device failure.
- 7. Vascular Access Complication: defined as AVF or AVG clotting during the dialysis procedure, bleeding for more than 30 minutes post-dialysis for 3 consecutive sessions, difficulty with vascular access resulting in inability to initiate or complete dialysis treatments or complications related to hemodialysis catheters (not including reduced blood flow in catheter or TPA or catheter exchange).
- 8. **Pyrogenic Reaction:** onset of objective chills (visible rigors) and fever (oral temperature greater than or equal to 37.5 degrees Celsius) in a Subject who was afebrile and who had no recorded signs or symptoms of infection before treatment.

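### The CEC is given a causal-attribution standard that does not fit endpoint item 1 (any SAE) alongside a definitional one, with no rule on which prevails

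*Protocol*

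**What the plan says.** **The endpoint.** Protocol 9.1.5 (repeated in 5.2 and the synopsis) lists eight kinds of event. Item 1 reads "Serious Adverse Event: any serious adverse event that" and continues with five seriousness outcomes. It carries no condition on cause. The adverse event definition beneath it, in 9.1.1, is neutral on cause: an event counts "whether it is considered to be related to the device or not".

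**What reaches the CEC.** Under 9.2.4, events that the site investigator judges device related, "severe in nature, and/or meets the definition of one the primary safety endpoint events, will be reviewed and adjudicated by a CEC". An SAE recognised as item 1 therefore goes to the CEC.

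**What the CEC is asked.** Section 9.2.4 sets the standard as "whether a reasonable attending nephrologist would attribute the AE to one of the causes listed as part of the Primary Safety Endpoint above". Later in the same paragraph the CEC also confirms that events put forward as endpoint events "do indeed meet the Safety Endpoint criteria". Section 6.4 gives a similar definitional task: to confirm whether the event belongs among the eight. It then lists relation to the device, to the dialysis procedure and to a pre-existing condition as further determinations.

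**The SAP.** The opening sentence of SAP 1.3 describes the primary safety endpoint as a count of pre-specified events that are also serious and related to the device. SAP 5.1 lists SAE as the first endpoint item with no such restriction.

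**The concern.** The CEC's decision determines the numerator of a primary endpoint, so the test it applies has to be the endpoint definition. Here the stated standard is a question about cause, while item 1 is the one item defined by seriousness alone. A hospitalisation for an unrelated illness meets item 1 but has no evident place on a list of causes. A panel that takes the sentence at its word could decline to confirm it.

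The direction of the error matters. Under Protocol 11.3, safety success depends only on how precisely the rate is estimated, and 11.8 gives the target as a 95% half-width below 1 event per 100 treatments. Leaving events out lowers the reported rate. If the variance rises with the rate, as in the Poisson-type model of Protocol 11.6 and SAP 5.2, it also narrows the interval. Both effects favour the device.

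**Working it through.** **1. Does the attribution test fit the items?** Some items contain a cause. Item 4 covers "hemolytic reactions due to disinfectant exposure, dialysate temperature, mechanical failure or other device related causes", and item 6 covers "a significant clinical event such as loss of consciousness, cardiac arrest, or seizure caused by device failure". So where the protocol wanted a causal limit, it wrote one. Item 1 ("any serious adverse event that" has one of the listed outcomes) has none.

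**2. Apply each text to one case:** an SAE hospitalisation unrelated to the device, the procedure or items 2 to 8.

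| Text | Test | Does the case count? |
|---|---|---|
| Protocol 5.2, 9.1.5 item 1 | Seriousness outcome met | Yes |
| Protocol 6.4, first task | One of the eight items | Yes |
| Protocol 9.2.4, confirmation sentence | Meets endpoint criteria | Yes |
| Protocol 9.2.4, adjudication standard | Attributed to a listed cause | No, if read literally |
| SAP 1.3, opening sentence | Serious and device related | No |
| SAP 5.1 | SAE, unrestricted | Yes |

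No text gives an order of precedence. Section 6.4 does not say whether relation to a pre-existing condition affects inclusion. SAP 5.1 and 5.2 do not say whether adjudicated or site-reported events are analysed.

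**3. Direction of the effect on the interval (illustration only).** The plan has no figure for adjudication to reproduce. Its own variance input cannot be used here. With 30 subjects × 32 treatments = 960 intervals, an SD of 0.8 per interval and AR(1) ρ = 0.50 (Protocol 11.8), the variance inflation is D = 1 + 2 Σ(1 − k/32)·0.5^k for k = 1 to 31, which is 2.875. The half-width is then 1.96 × 0.8 × √(2.875/960) × 100 = 8.58 per 100, not below 1. That is a separate matter. A fixed SD would in any case not respond to the number of events.

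I therefore use Poisson variance: half-width = 1.96 × √(r × D/960) × 100, where r is the rate per interval, D = 2.875 under AR(1) and D = 1 under independence. The rates and the shares removed are assumptions.

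| Assumed rate per 100 | Share removed | Rate left | Half-width, AR(1) 0.5 | Half-width, independent |
|---|---|---|---|---|
| 1.0 | 0% | 1.00 | 1.07 | 0.63 |
| 1.0 | 25% | 0.75 | 0.93 | 0.55 |
| 2.0 | 0% | 2.00 | 1.52 | 0.89 |
| 2.0 | 25% | 1.50 | 1.31 | 0.77 |
| 2.0 | 50% | 1.00 | 1.07 | 0.63 |
| 2.5 | 0% | 2.50 | 1.70 | 1.00 |
| 2.5 | 25% | 1.875 | 1.47 | 0.87 |
| 2.5 | 75% | 0.625 | 0.85 | 0.50 |

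For example, at 1 per 100 there are 9.6 expected events per period. Removing a quarter leaves 7.2, and the AR(1) half-width moves from 1.07 to 0.93.

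**4. What this shows.** Rate and half-width both fall whenever events are removed. Whether the half-width crosses 1 depends entirely on the assumed rate, share and correlation.

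**The case against.** The best defence is that the word for causes in 9.2.4 is loose drafting for the eight categories. The only list above that sentence is 9.1.5, most entries on it are kinds of event rather than causes, and item 1 on it is any SAE. On that reading the unrelated hospitalisation is assigned to item 1 and counts. Section 6.4, the confirmation sentence in 9.2.4, the two-way categorisation in 9.2.1 and SAP 5.1 all agree with it. SAP Tables 20 and 21 count SAEs as an endpoint item and report device relationship separately.

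Much of this stands. A reader might infer that the CEC will necessarily drop unrelated SAEs. The documents do not support that, because they contain a definitional test as well. A reader might also infer that SAEs are the largest part of the endpoint. No document gives frequencies by item; all that can be said is that item 1 is the only item defined by seriousness alone. Nor can it be inferred that the exclusion would carry the study over its precision criterion. At an assumed 2.5 per 100 with independent intervals, the half-width starts at 1.00, so almost any removal appears to pass. Under the plan's own AR(1) correlation it goes from 1.70 to 1.47 after a 25% loss and still fails.

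The defence does not remove the point. The literal reading remains available, nothing ranks the two tests, and the opening sentence of SAP 1.3 supports anyone who takes the endpoint to be restricted by cause.

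**Conclusion.** The inconsistency is real and should be corrected. The protocol gives the CEC two unreconciled tests for the same decision, one of which does not fit item 1, and SAP 1.3 describes a third, narrower endpoint. Read literally, either the attribution standard or the SAP 1.3 wording could exclude SAEs that 9.1.5 counts. The bias would be towards a lower reported rate and, if variance rises with the rate, a narrower interval.

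The size cannot be determined from the documents: they give neither event rates by item nor the share of SAEs without a listed cause. The half-widths above show direction only. They rest on assumed rates and shares, Poisson variance, and 960 intervals per period.

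**What to change.** - **Protocol 9.2.4:** replace the attribution sentence. The CEC decides only whether the event meets the written definition of at least one of the eight items in 9.1.5, and for item 1 meeting a seriousness criterion is sufficient.
- **Protocol 6.4 and 9.2.4:** record relationship to the device, the procedure or a pre-existing condition separately, as 6.4 already lists, and state that it does not remove an event from the endpoint. Section 6.4 ties the procedure determination to classification as an additional treatment observation, so the statement should cover that case.
- **SAP 1.3:** delete the restriction to serious, device-related events from the opening sentence, so that it matches SAP 5.1 and Protocol 9.1.5.
- **SAP 5.2:** it would help to name the event source for the primary analysis and to report site-reported and adjudicated counts side by side.

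The cost is a few sentences across the two documents, with no new data collection and no change in sample size. If events have already been adjudicated under the present sentence, any SAEs not confirmed would need to be rechecked against item 1. The downside for the sponsor is that the reported rate may be less favourable.

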9.3 Reporting Requirements of SAEs or UADEs

The Investigator must report all SAEs or UADEs immediately upon awareness to Outset. The site should contact the following person by telephone to provide the initial notification:

> [name] Vice President, Commercial and Corporate Strategy [name] [contact] [contact] (cell)

The Investigator must follow up the initial telephone notification by providing a written report by facsimile or mail describing the SAE or UADE to Outset. This report may be accomplished by completing the AE CRF. Any missing or additional relevant information concerning the SAE or UADE should be provided in the form of a written follow-up report.

The Investigator is required to comply with applicable regulations regarding the notification of SAE/UADE to the reviewing IRB consistent with any IRB conditions of approval.

RISKS AND BENEFITS 10

10.1 Potential Risks

The potential risks and benefits of participation in this study are identified in the Subject Informed Consent Form (ICF) and are to be explained to the Subject and/or their legal representative prior to participating in the study. It is not anticipated that there will be any additional risks to the Subject with use of the Tablo[™] System that are different than those expected during routine dialysis procedures.

10.1.1 Procedure Risks

Potential adverse events that may be associated with a hemodialysis procedure include, but are not limited to, the following:

- Abdominal pain
- Adynamic bone disease
 - Air embolism
- **Epigastric fullness** Fatigue
- Fever

- Occult hemorrhage
- Pain .
 - Pericardial tamponade

TABLO Clinical Study Study# 2014-01 Amendment 9, dated January 9, 2020 DOC-0000876, Rev 11

Page 28 of 40

Outset Medical

CONFIDENTIAL

Perspiration

Pruritus

Seizures

Septicemia

Sleep apnea

Thrombosis

Tremors

Uremia

Vomiting

Weakness

Weight gain

Weight loss

Wheezing

Syncope

Tetany

Slurred speech

Pneumothorax

Pulmonary edema

Sexual dysfunction Shortness of Breath

Thrombocytopenia

Uremic encephalopathy

Vascular access complications

Uremic neuropathy

Vascular calcification

Restless leg syndrome

.

•

•

٠

•

•

•

.

.

•

•

•

.

.

٠

٠

- Allergic reaction •
- Allergic skin reactions
- Aluminum toxicity
- Anaphylaxis
- Anemia
- Angioedema
- Anuria
- Anxiety
- Arrhythmia
- Ascites
- Atlanto-cervical spondylopathy
- Back pain
- Bleeding complications from the use of blood thinners
- Bleeding from access
- Cerebrovascular disease
- Chest pain
- Chills/Rigors
- Chronic dementia
- Circumoral paresthesia
- Cold extremities
- Colitis
- Complement activation
- Confusion
- Congestive heart failure
- Constipation
- Cough
- Cramps
- Depression
- Dialysis-associated neutropenia
- **Dialyzer** reaction
- Diarrhea
- **Difficulty swallowing**
- Digestion or absorption disorders
- Disequilibrium syndrome
- Dizziness
- Edema
- **Electrolyte Imbalance**

There may be other potential risks that are unforeseen at this time.

10.2 Risk Management Procedures

Eligibility criteria have been selected that exclude Subjects who are at a higher risk for experiencing an anticipated adverse event in order to reduce the risks to Subjects who participate in this study. In addition, Subjects enrolled in this study will receive their hemodialysis treatments by qualified dialysis center staff when undergoing treatments In-Center and will perform their own hemodialysis treatments after having completed device study training when performing treatments In-Home.

Monitoring will take place throughout the course of treatment and adverse events will be recorded in the Subject's charts and on Case Report Forms developed for the study.

- Fluid overload •
- Hallucinations •
- Headaches •
- Heart palpitations •
- Hematoma

•

- Hemolysis
- Hemothorax •
- Hepatitis B
- Hepatitis C •
- Urticaria
- Hyperparathyroid bone disease •
- Hyperparathyroidism
- Hypertension
- Hypoglycemia •
- . Hypotension
- Hypovolemia
- Hypoxemia
- Ileus
- Infection
- Inflammation
- Insomnia
- Intracranial bleeding
- Iron deficiency
- Ketoacidosis
- Lactic acidosis
- Left ventricular hypertrophy
- Lipid abnormalities •
- Liver function abnormalities
- Loss of consciousness •
- Malnourished .
- .
- Monomeuropathies
- Myocardial infarction
- Nasal congestion
- Nausea

- Page 29 of 40

- Neutropenia

- Metabolic acidosis/alkalosis
- Metabolic disorders

In addition, engineering testing has been performed on the Tablo[™] System to help mitigate any risks to the Subjects due to product failure.

Investigational device training will be conducted at each initiated study center and appropriate training records will be maintained.

10.3 Potential Benefits

There are no guaranteed additional benefits from participation in this study; however, dialysis with the Tablo[™] System is expected to provide the Subject with the required urea clearance. Information gained from the conduct of this study may be of no benefit to others with the same medical condition.

11 STATISTICAL METHODS AND CONSIDERATIONS

The Statistical Analysis Plan (SAP) for the study will describe the data sets to be analyzed, the methods of analysis, and the specific analyses to be conducted in support of the study's primary endpoints. Those key elements are outlined below.

11.1 Data Sets Analyzed

All Subjects who meet all of the Inclusion and Exclusion Criteria and who start the **first study treatment** during the **first treatment period** will be considered enrolled and will be included in the Intent-to-Treat Population (ITT). The primary effectiveness endpoint analysis will be based on the ITT population with a supportive analysis for the Per-Protocol population (PP).

11.1.1 Intent to Treat Population (ITT)

The ITT population will consist of all Subjects who are enrolled in the study. The primary analysis set will be the ITT analysis set with no missing value imputation with a sensitivity analysis performed on the ITT with missing value imputation population.

11.1.2 Per Protocol Population (PP)

The PP population will consist of all Subjects who are enrolled in the study, have successfully completed at least 75% of their dialysis treatments, have at least one valid value of the primary effectiveness variable and have no major protocol deviations while enrolled in the study. A successfully completed dialysis treatment is defined as one completed as prescribed by the physician. A major protocol deviation is defined as any protocol deviation that affects the soundness of the data or a Subject's rights. Subjects to be excluded from the PP analysis set, and the reasons for their exclusion, will be determined and documented prior to statistical analysis. These decisions will not be outcome-data driven.

The analysis of the primary efficacy endpoint will be conducted on ITT and PP populations.

11.2 Safety Population

The safety population will consist of all Subjects who are enrolled in the study. All safety analyses will be conducted on the safety population.

11.3 Analysis of Primary Endpoint

The study is based on the primary endpoints for effectiveness and interval estimates of the safety of the device. The study will be considered a success from a statistical standpoint if:

- 1. Both primary analysis variables pass their respective hypotheses, i.e., H_{a0} and H_{b0} below are rejected in favor of H_{a1} and H_{b1}, respectively,
- 2. The rate of pre-specified adverse events per dialysis interval is estimated to be within the specified error of estimation for each treatment period.

11.4 Analysis of Weekly Standardized Kt/V

The following hypotheses will be tested at a one-sided α =0.025 level of significance:

$$H_{a0}$$
: $\mu_{IC} \le 2.1$ vs. H_{a1} : $\mu_{IC} > 2.1$

and

H_{b0}: $\mu_{IH} \leq 2.1$ vs. H_{b1}: $\mu_{IH} > 2.1$

where μ_{IC} is the treatment period mean weekly standardized Kt/V value for the In-Center arm and μ_{IH} is the treatment period mean weekly standardized Kt/V value for the In-Home arm. This hypothesis will be tested using the Least Square Mean for the respective treatment period from a repeated measures analysis of variance (RMANOVA) containing terms for Subject, arm and time points (weeks) and using an AR(1) covariance structure.

The weekly standardized Kt/V value will be calculated using the Leypoldt (Seminar in Dialysis, 17(2); March-April 2004) formula of:

Standard Kt/V (stdKt/V) = 168*(1-exp(-Kt/V))/t/((1-exp(-t/V))/(Kt/V)+168/(N*t) -1)

Where: N=number of treatments / week; t= treatment time in hours

Summary statistics (mean, sample size, standard deviation, minimum, maximum, and median) will be computed on the weekly standardized Kt/V values for each treatment period.

11.5 Analysis of Secondary Endpoint

The analysis of the secondary endpoint of ultrafiltration rate (UFR) will be conducted on ITT and PP populations. The UFR will be calculated using the following method:

UF Rate = (Fluid Removal Goal + Rinse Back Volume) / Treatment Duration

Where,

Fluid Removal Goal = Today's Weight – Prescribed Estimated Dry Weight

And,

Rinse Back Volume = The volume of saline, 300mL, returned to the patient at the end of treatment.

11.6 Analysis of Adverse Events

All study-emergent AEs occurring during the study sessions will be recorded and classified on the basis of MedDRA terminology for the ITT population. Study-emergent AEs are those AEs with an onset on or after the date of first study treatment. All study-emergent AEs will be categorized by study period (In-Center or In-Home), the number of Subjects reporting study-emergent AEs, severity, device relationship, and seriousness. Serious adverse events (SAEs) will be listed by Subject. SAEs will be categorized by study period, severity, and device relationship. Each Subject will be counted only once within a category using the event with the greatest device relationship and greatest severity.

For each treatment period, a 95% confidence interval will be computed on the pre-specified adverse event rate per dialysis interval. This confidence interval will be computed using the Least Square Mean for the respective treatment period from a generalized linear model containing terms for Subject, arm and time points (i.e., a repeated measures analysis using GEE) using a Poisson link function and AR(1) covariance structure.

Summary statistics (mean, sample size, standard deviation, minimum, maximum, median) will be computed on the number of pre-specified adverse events per dialysis interval for each treatment period. The same summary statistics will be calculated by treatment period for the rate of pre-specified adverse events per 100 dialysis treatments.

